Study Title: Comparative Tests of Flu Vaccination Phone Messages

Summary of Research Protocol

October 30, 2017

This project is an unfunded research collaboration between Emmi Solutions, Inc., and a team of academic research investigators led by [name]. of the University of Michigan.

Emmi Solutions provides services that educate, support, remind, and ultimately prompt people to take actions toward better health on behalf of various clients, which include individual physicians or medical practices, hospital systems, and health insurance companies. As part of their service to their clients, Emmi deploys outbound, automated, Interactive Voice Response phone calls with the outlined variations to patients identified by Emmi's clients as eligible for the flu vaccine.

This study will begin by gaining consent from specific clients of Emmi Solutions to share de-identified data collected on their patient populations with the investigators for the purpose of investigating the effectiveness of different telephone scripts at promoting behavioral intentions related to vaccination.

Calls will be made at times and at a rate specified by Emmi's clients using Emmi's in-house automatic deployment system. Pre-recorded messages that adjust to patient responses will follow interaction outlines, or "scripts" developed by Emmi for the purpose of encouraging uptake of seasonal influenza vaccination. Contact information and basic demographic information about each patient is provided by the client based on their own processes and is confidentially maintained by Emmi as part of their services.

Within each client's list of patients, Emmi will randomly assign patients to receive different versions of the flu call script. Patients of larger clients will be randomized among the full set of experimental arms, while patients of smaller clients may be randomized among a smaller subset of arms to ensure statistical power for comparisons within each client's patient set, with the decision to be based on the size of the provided patient list.

As part of Emmi's standard process, each call includes one or more questions that recipients can answer during the call (e.g., by saying "yes" to the question). For the calls included in this study, at least one question will measure patients' behavioral intentions to receive an influenza vaccine.

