Emmi's database records each patient's responses over the course of the call and generates one report of all patients' responses for Emmi's clients to review. This report includes Protected Health Information, such as patient names and phone numbers.

As part of this research, however, Emmi will then de-identify the reports to meet the standards of the Health Insurance Portability and Accountability Act and then send the de-identified response reports, as well as linked demographic information and call timing data, and send them to the investigators via Secure File Transfer Protocol, the preferred trusted protocol used between Emmi and their clients. Each patient record will not include any Protected Health Information and will be identified only by a unique identification number. Only Emmi will maintain and have access to the mapping algorithm that could enable matching of individual records to contact information or other protected health information.

Certain clients of Emmi also have access to other information about their patients, such as data that may indicate whether a patient actually obtains an influenza vaccination during the 2017-2018 influenza season. If clients share these data with Emmi, Emmi will in turn share with investigators (again, only using the unique patient id number and secure file transfer) for inclusion of these variables in analyses.

The research investigators (led by [name]) will then conduct statistical analyses to determine if the rates of behavioral intentions to vaccinate (and actual vaccination status, when available) differed among the study arms. After preliminary bivariate analyses (e.g., chi-squared analyses), logistic regression analyses will control for variation among clients (both because client populations vary in unmeasured ways and because call timing will be different for different clients) and include available demographic information when possible.

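### The planned regression handles call timing only through client; adding a simple call-date term would recover a little power at almost no cost

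*Combined protocol and SAP*

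**What the plan says.** The Summary of Research Protocol has no numbered sections. Four places in it bear on this point.

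- **Analysis (final paragraph).** After preliminary bivariate tests, "logistic regression analyses will control for variation among clients". Two reasons are given: unmeasured differences between client populations, and timing, "because call timing will be different for different clients". The only other covariates named are demographic: the models will "include available demographic information when possible".
- **Data transfer.** The investigators receive the de-identified response reports "as well as linked demographic information and call timing data". Each patient record "will be identified only by a unique identification number".
- **Call deployment.** "Calls will be made at times and at a rate specified by Emmi's clients".
- **Randomisation.** "Within each client's list of patients, Emmi will randomly assign patients to receive different versions of the flu call script".

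The plan neither names a call date, week or time term for the regression nor rules one out. It does not give the length of any client's calling window, and it does not say whether intention changes with call date within a client.

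**The concern.** The plan treats timing as worth controlling for, but adjusts for it by proxy. A client term, whether fixed, random or stratified, removes only the average timing difference between clients. If a client spreads its calls over several weeks of the influenza season, patients called early and late share the same client term, and any change in their readiness to vaccinate goes unmodelled.

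In a logistic model, omitting a prognostic covariate that is balanced between arms has two linked effects: the estimated odds ratio moves toward 1, and the test of the script effect loses some power. There is also a small pre-specification gap. Timing data will be in hand, but the plan does not say whether or how they enter the model, so that choice could be made after results are seen.

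**Working it through.** The plan states no sample size, event rate, effect size, alpha or power, so it has no figure to reproduce. Every rate below is an assumption.

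**Step 1: cost of omitting a balanced call-time covariate.** Let call time be uniform over a client's calling window, with intention p moving linearly on the logit scale from s at the start to e at the end. Write d = logit(s) − logit(e). Then:

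- mean of p(1−p) over the window = (s − e)/d
- mean intention p̄ = ln[(1 − e)/(1 − s)]/d
- relative efficiency RE of the model without call time = mean of p(1−p), divided by p̄(1 − p̄)
- sample-size-equivalent cost = 1/RE − 1
- power without the term = Φ[(1.960 + 0.842)·√RE − 1.960], when the model with the term has 80% power at two-sided alpha 0.05

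Worked example, 50% to 20%:

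- d = 0 − (−1.3863) = 1.3863
- mean of p(1−p) = 0.30/1.3863 = 0.2164
- p̄ = ln(0.80/0.50)/1.3863 = 0.339, so p̄(1 − p̄) = 0.2241
- RE = 0.2164/0.2241 = 0.9657
- cost = 1/0.9657 − 1 = 3.6%
- power = Φ(2.802 × 0.9827 − 1.960) = Φ(0.793) = 78.6%

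The last column of the table is the log odds ratio without the term divided by the log odds ratio with it, at an assumed conditional odds ratio of 1.3. Entries come from unrounded values.

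| Assumed fall in intention | p̄ | RE | Sample-size-equivalent cost | Power (80% with term) | Log-OR ratio |
|---|---|---|---|---|---|
| 35% to 30% | 0.325 | 0.9990 | 0.1% | 80.0% | 0.9990 |
| 40% to 30% | 0.349 | 0.9963 | 0.4% | 79.9% | 0.9962 |
| 40% to 20% | 0.293 | 0.9838 | 1.7% | 79.4% | 0.9829 |
| 50% to 20% | 0.339 | 0.9657 | 3.6% | 78.6% | 0.9645 |
| 50% to 10% | 0.268 | 0.9291 | 7.6% | 77.0% | 0.9253 |
| 60% to 10% | 0.312 | 0.8956 | 11.7% | 75.5% | 0.8915 |
| 70% to 5% | 0.304 | 0.8102 | 23.4% | 71.3% | 0.8035 |

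A short calling window means s is close to e, so RE is close to 1 and the cost is close to zero.

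**Step 2: validity.** A simulation used 4 clients, 2 scripts assigned 1:1 independently of call time, 2,600 patients in total, intention falling from 50% to 20% over the window (shifted up or down by client), and 1,500 replicates.

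- No script effect: type I error was 4.4% with client only and 4.4% with client plus call time. The Monte Carlo standard error is √(0.044 × 0.956/1500) = 0.5 percentage points.
- True conditional log odds ratio 0.239 (odds ratio 1.27): the mean estimate was 0.235 with client only and 0.242 with call time. Power was 81.8% and 82.8%.

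The error rate is unaffected, and the gain in power is small.

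**The case against.** The strongest reply is that nothing here is invalid. Scripts are randomised within each client's list, so unless calls are scheduled by script, call date is independent of script within a client. Chance imbalance in call date is ordinary random variation, already covered by the test's error rate. Timing could confound between clients, because smaller clients may use fewer scripts, and the planned client adjustment addresses that. All of this stands.

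A reader might infer more from the gap than the documents support, in three ways:

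- **That script comparisons are biased or their error rate inflated.** Randomisation within client rules this out if call order does not depend on script. The documents do not say either way about call order, so it needs confirming, but nothing suggests a dependence.
- **That seasonal drift within clients is established.** A client-set rate makes a spread of call dates possible. Neither the spread nor its effect on intention is given.
- **That the plan rejects a timing term.** It is a summary that names some covariates and excludes none. Even patient-level timing is inferred, from transfer alongside individually numbered records.

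The reply also limits the remedy. The documents do not mention a first-attempt date. Week categories that differ by client would be expensive: with an assumed 10 clients and 8 weeks, they add 10 × (8 − 1) = 70 parameters, with sparse cells in smaller clients.

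The reply does not remove the central point. The plan gives timing as a reason to adjust, expects to hold timing data, and names a proxy that cannot capture variation within a client.

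**Conclusion.** The point holds as a minor improvement in efficiency and pre-specification; it does not correct an error. For assumed falls in intention of up to 50% to 20% over a client's calling window, leaving call date out costs at most 3.6% in sample-size terms (power 78.6% against 80%) and shrinks the log odds ratio by less than 4%. Costs of 7.6% or more arise only for declines of 40 percentage points or greater among those examined.

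These figures assume calls spread evenly over the window, a steady decline on the logit scale, and call order independent of script. They concern the regression comparisons. The preliminary bivariate tests, which as described do not adjust even for client, raise a separate question.

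**What to change.** Add one sentence to the analysis paragraph: the logistic models for intention and for vaccination will include call date (calendar date or study week) beside client and script, as a linear or simple smooth term common to all clients.

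Use the date of the first scheduled or attempted call if that field is supplied, because the date of an answered call may reflect who picks up. Check with the company making the calls that the transfer holds a date for each patient and which date it is. Also have it confirm that the order of calls within a client's list does not depend on the assigned script, and state this in the plan. Do not use client-by-week categories by default.

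The cost is a sentence, a check of the data fields, and one or a few degrees of freedom.
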